3.3. ENROLLMENT

Approximately 60 patients who have undergone allo BMT for B-cell derived hematologic malignancies.

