6. STUDY STATISTICS

This is a phase I study of Idelalisib, an orally-administered, selective inhibitor of Phosphoinositide 3 kinase (PI3K)- δ . It has been successfully used pre-transplant to induce partial and complete responses in many B-cell derived malignancies. In this study Idelalisib will be evaluated in the post-transplant setting. Patients receiving a standard of care allogeneic hematopoietic stem cell transplant from any source: cord, marrow, or peripheral blood will be eligible. Patients will be randomized in a 2:1 ratio to either 100 mg Idelalisib twice daily from day 90 (\pm 10 days) following transplant, Arm A, or a placebo, Arm B, and monitored for toxicity until day 270.

Study treatment plan: Idelalisib day +90 [+/- 10 days), 100mg twice daily, and at least 5 days after the discontinuation of filgrastim if ANC is greater than 1,000 and PLT 50>Gi/L and <grade 2 aGVHD. Patient's Idelalisib will be dose adjusted for the expected toxicities of Idelalisib including pneumonitis, hepatitis, neutropenia, thrombocytopenia and loose stools.

Primary endpoint and design: The primary goal of this study is to evaluate the safety of Idelalisib as post-transplantation maintenance in patients undergoing an allogeneic BMT. In addition to the allowed dose reductions, a safety monitoring plan will be implemented to ensure that other treatment-limiting events are not elevated. The study will be monitored between the date of randomization and day 270 post-transplant. For safety monitoring, treatment-limiting toxicities will be defined as Idelalisib interruption for >14 days, or other grade 3 or higher adverse events as defined by CTCAE IV not captured in the protocol for dose de-escalation. The trial will assume that, *a priori*, the probability of these events in both arms of the study will follow a Beta (0.10, 0.90) prior distribution. This distribution corresponds to an assumption that 10% of patients might experience a treatment-limiting toxicity.

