Sample size/accrual Rate: The accrual rate for this study is expected to be 20 patients per year. The total sample size will be 45 patients, 30 on the Idelalisib arm (Arm A) and 15 on the control arm (Arm B). The safety objective of this trial is based on the precision of estimating the specified treatment-limiting toxicity events. An approximation to the precision will be made using binomial confidence intervals. Thirty patients on the Idelalisib arm will allow us to estimate the proportion of patients experiencing post-transplant events with a precision of $\pm 0.19\%$.

Interim analyses and operating characteristics: For monitoring we will compute the posterior probability of a treatment-limiting toxicity between day 90 and 270 in each arm of the study, given the data and prior distribution, Beta(0.10, 0.90), and evaluate whether to hold accrual after fixed cohorts of patients. Monitoring will occur in groups of 15 patients, beginning after the first 10 enrolled on Arm A. The maximum sample size will be 45 patients, 30 in Arm A and 15 in Arm B. The stopping rule will recommend a safety review if it becomes clear that the posterior probability of a treatment-limiting toxicity in Arm A exceeding Arm B by 0.10 is 75% or greater. Operating characteristics of the study with Arm B treatment-limiting toxicity of either 5%, Table 1, or 10%, Table 2, and varying toxicities in Arm A are based on 1,000 simulations of the trial.

Table 1. Scenarios with control arm (Arm B) treatment-limiting toxicity of 5%
Both arms prior: Beta (0.10, 0.90), assumes prior for toxicity is 10%, delta of 0.10, and 75% cutoff.
2:1 randomization Total N=45

	Delta=0.10	Delta=0.10
Scenario: Control, Idelalisib	Stopped for toxicity	Avg. sample size Control, Idelalisib
1: 0.05, 0.05	1.3%	14.9, 29.8
2: 0.05, 0.10	6.8%	14.4, 28.8
3: 0.05, 0.15	19.2%	13.4, 26.8
4: 0.05, 0.20	32.4%	12.3, 24.7
5: 0.05, 0.25	53.1%	10.5, 21.0
6: 0.05, 0.30	68.2%	9.3, 18.7
7: 0.05, 0.35	82.3%	8.0, 16.0
8: 0.05, 0.40	89.8%	7.1, 14.2
9: 0.05, 0.45	94.9%	6.3, 12.6

Table 2.

Scenarios with control arm (Arm B) treatment-limiting toxicity of 10%

Both arms prior: Beta(0.10, 0.90), assumes prior for toxicity is 10%, delta of 0.10 and 75% cutoff.

2:1 randomization Total N=45

	Delta=0.10	Delta=0.10
Scenario: Control, Idelalisib	Stopped for toxicity	Avg. sample size Control, Idelalisib
1: 0.10, 0.10	4.9%	14.6, 29.1
2: 0.10, 0.15	12.0%	13.9, 27.8
3: 0.10, 0.20	27.9%	12.7, 25.4
4: 0.10, 0.25	44.3%	11.4, 22.8

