5: 0.10, 0.30	59.0%	10.1, 20.2
6: 0.10, 0.35	70.7%	9.3, 18.5
7: 0.10, 0.40	83.4%	8.1, 16.1
8: 0.10, 0.45	90.0%	7.3, 14.5
9: 0.10, 0.50	94.4%	6.6, 13.1

Secondary endpoint:

1. Event-free survival at one year.

Analysis Plans:

Toxicities will be summarized descriptively by grade and type. Cumulative incidences of aGVHD, relapse, and NRM will also be computed using Fine and Gray's method for competing risks. Treatment of relapse/progression, graft failure, and death are considered competing risks for GVHD; relapse/progression is a competing risk for NRM; and death before relapse/progression is a competing risk for relapse/progression. In addition, we plan to report aGVHD incidences with only graft failure and death regarded as competing risks.

Using the Kaplan-Meier method, the probability of 1-year event-free survival will be estimated and reported with 95% confidence intervals. The proportions of patients who are event-free at 1 year will also be estimated with a 95% exact binomial confidence interval.

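### The precision printed for 30 idelalisib patients (±0.19%) is about 100 times too small, and the enrolment figures of about 60 and 45 are not reconciled

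*Combined protocol and SAP*

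**What the plan says.** Section 6 (Study Statistics), under sample size and accrual, makes precision the footing of the safety objective: "The safety objective of this trial is based on the precision of estimating the specified treatment-limiting toxicity events". It adds: "An approximation to the precision will be made using binomial confidence intervals". For the 30 patients in Arm A it then claims to "estimate the proportion of patients experiencing post-transplant events with a precision of $\pm 0.19", with a percent sign directly after the number. The sentence gives no confidence level, does not say whether the interval is exact or approximate, and names no event rate.

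Two other statements in Section 6 bear on how the figure might have been obtained. The analysis plan names a level and a method, but for a different endpoint, event-free survival: "The proportions of patients who are event-free at 1 year will also be estimated with a 95% exact binomial confidence interval". The design paragraph gives a rate for treatment-limiting toxicity when it describes the prior: "This distribution corresponds to an assumption that 10% of patients might experience a treatment-limiting toxicity".

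On the number of patients, Section 3.3 reads: "Approximately 60 patients who have undergone allo BMT for B-cell derived hematologic malignancies". Section 6 reads: "The total sample size will be 45 patients, 30 on the Idelalisib arm (Arm A) and 15 on the control arm (Arm B"), and for the interim monitoring: "The maximum sample size will be 45 patients, 30 in Arm A and 15 in Arm B". Both operating-characteristic tables are headed with a total of 45.

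**The concern.** A half-width of 0.19% means that the true toxicity rate would be known to within about a fifth of a percentage point, which 30 patients cannot deliver. This is the only number offered in support of the stated basis of the safety objective, so it should be correct and a reader should be able to reproduce it. As printed, neither is so.

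The enrolment conflict is a separate matter. A protocol needs one planned number of patients. Section 3.3 exceeds the Section 6 maximum by 15, and it does not say whether its 60 counts patients consented, screened, randomised or treated.

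**Working it through.** **Inputs.** From Section 6: n = 30 in Arm A; a 10% toxicity rate (the prior mean); 2:1 allocation; total and maximum 45; accrual of 20 per year. From Section 3.3: about 60. Assumed, because the plan does not say: 95% confidence as the main case, with 80% to 99% also tried, and a 50% rate as the widest case.

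**1. Can ±0.19% (0.0019) be reproduced?** No.

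- Half-widths were computed at n = 30 for 0 to 30 events with the Wald, Wilson, Agresti-Coull, Jeffreys and Clopper-Pearson (exact) methods. The zero-width Wald interval at 0/30 and 30/30 was left out.
- The smallest at 95% is Jeffreys at 0/30: 0.040, and 0.040 / 0.0019 ≈ 21 times the printed figure. At 80% the smallest is 0.022.
- The posterior interval from the plan's own Beta(0.10, 0.90) prior is narrower still at 0 events: 0.0158 at 95% and 0.0044 at 80%. Even 0.0044 is more than twice 0.0019.
- Number needed for a 95% Wald half-width h = 0.0019, from n = 1.96² p(1 − p) / h² (unrounded z): 266,029 at p = 0.5 and 95,770 at p = 0.1, before rounding up.

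**2. Do the digits fit a proportion of 0.19?** Yes, but on more than one basis (n = 30).

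| Basis | Half-width |
|---|---|
| 95% exact, 15/30 (0.313 to 0.687) | (0.687 − 0.313)/2 = 0.187 |
| 95% Wald, p = 0.5 | 1.96 √(0.25/30) = 0.179 |
| 95% Jeffreys, 15/30 | 0.172 |
| 95% Wilson, 15/30 | 0.168 |
| 90% exact, 15/30 | 0.161 |
| 99% Wald, p = 0.2 | 2.576 √(0.16/30) = 0.188 |
| 99% exact, 6/30 | 0.194 |

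The worst-case exact 95% half-width rounds to 0.19. So do the 99% Wald and exact half-widths at a 20% rate. If precision means the distance from the estimate up to the upper exact 95% limit, every count from 6/30 (0.186) to 15/30 (0.187) also rounds to 0.19.

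The worst-case exact 95% reading points to an arm of 30. With 60 patients split 2:1, Arm A would have 40, and that half-width would be 0.162.

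**3. What is the precision at the plan's own rate?** For 3/30 (10%), the exact 95% interval is 0.0211 to 0.2653. It extends 0.1000 − 0.0211 = 0.079 below the estimate and 0.2653 − 0.1000 = 0.165 above it. The half-width is (0.2653 − 0.0211)/2 = 0.122, or 0.107 by Wald. Averaged over the possible counts at a true 10% rate, the exact half-width is 0.118.

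**4. Enrolment.** 60 − 45 = 15, and 15/45 = 33%. At 20 per year, 45 patients take 2.25 years and 60 take 3.0 years. Since 45/(1 − 0.25) = 60, a 25% loss would link the two numbers, but no dropout, replacement, screen-failure or consent-loss rate of that size appears in the document.

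**The case against.** The strongest reply is that the precision figure is a slip of units on which nothing depends. The stopping rule, its simulations and the 30:15 split do not use it, and no reader would believe ±0.19% from 30 patients. That is right about the consequences. It is why the point calls for a wording change and no redesign. Correcting the unit would still leave the figure irreproducible, because 0.19 fits several combinations of level, method and rate. For the same reason the exact 95% interval at 50% should not be written in as fact; the statistician has to confirm the basis.

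The percent sign could have come from converting the file to text. That cannot be excluded from the text alone, so the PDF should be checked, although an added percent sign seems less likely than an authoring slip. The missing level, method and rate do not depend on it.

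The 10% rate is the mean of a monitoring prior, and the plan never says that precision was evaluated there. The interval at 3/30 is therefore a useful addition, not a correction of something the plan claimed.

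On enrolment, Section 6 calls 45 the maximum, so 45 probably governs. A gap between consent and treatment is also plausible: Section 10.2 places consent between Day +60 and Day +100, while Section 4 starts drug at about Day +90, subject to blood counts and filgrastim timing. But no passage says that 60 are to be consented so that 45 can be randomised. The explanation is conjecture, and the need for a clarifying sentence stands.

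**Conclusion.** Both parts hold. As printed, ±0.19% is wrong for 30 patients. Read as a proportion of 0.19 it is about 100 times too small, and even the narrowest non-degenerate 95% interval of the five standard methods is about 21 times wider. That the intended figure is the worst-case exact 95% half-width (0.187) is a reasonable inference that assumes a 95% level, an exact method and a 50% rate, none of which the sentence states. That no standard interval gives ±0.19% does not depend on this inference.

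The enrolment figures conflict by 15 patients, a third of 45, and the text does not connect them. The conflict shows that the protocol is unclear; it does not prove that more than 45 patients are meant to be randomised.

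This should be fixed, but it does not undermine the monitoring design.

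**What to change.** In Section 6, replace the printed precision with ±0.19 (19 percentage points). The trial statistician should confirm that value and state the confidence level, the interval method, the assumed event rate and, if the figure is not a half-width, what precision means. Add the exact 95% interval at the plan's own 10% rate: 2.1% to 26.5% for 3/30 events.

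Reconcile Section 3.3 with Section 6 in one of two ways: state 45 randomised (30:15) in Section 3.3, or define 60 as the number consented or screened, with 45 as the randomised maximum.

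The cost is a wording change and the statistician's confirmation, with no new data, patients or simulations. The stated precision will look less favourable than the one now printed.

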9. ADVERSE EVENTS

9.1. OVERVIEW

The Principal Investigator is responsible for the detection and documentation of events meeting the criteria and definition of an AE (adverse event) or SAE (serious adverse event) as described in this protocol. All AEs and SAEs will be recorded in the source documents and on the appropriate electronic CRF(s). All data will be reviewed periodically by the SKCCC Safety Monitoring Committee (SMC), which may provide recommendations about withdrawing any participant and/or terminating the study because of safety concerns.

Adverse events that are classified as serious according to the definition of health authorities must be reported promptly and appropriately to the Principal Investigators in the trial, IRBs and health authorities. This section defines the types of AEs and outlines the procedures for appropriately collecting, grading, recording and reporting them. Information in this section complies with *21CFR 312; ICH Guideline E2A: Clinical Safety Data Management: Definitions and Standards for Expedited Reporting; and ICH Guideline E-6: Guidelines for Good Clinical Practice*; and applies the standards set forth in the National Cancer Institute (NCI), *Common Terminology Criteria for Adverse Events, Version 4.0 (May 28, 2009)*.

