9.4. GRADING AND ATTRIBUTION OF ADVERSE EVENTS

9.4.1 Grading Criteria

The study site will grade the severity of AEs experienced by study participants according to the criteria set forth in the National Cancer Institute's ***Common Terminology Criteria for Adverse Events Version 4.0*** (published May 28, 2009). This document (referred to herein as the "NCI-CTCAE v. 4.0 manual") provides a common language to describe levels of severity, to analyze and interpret data, and to articulate the clinical significance of all AEs.

Severity of adverse events will be graded on a scale from 1 to 5 according to the following standards in the NCI-CTCAE v. 4.0 manual:

- Grade 1 = mild adverse event.
- Grade 2 = moderate adverse event.
- Grade 3 = severe and undesirable adverse event.
- Grade 4 = life-threatening or disabling adverse event.
- Grade 5 = death.

For additional information and a printable version of the NCI-CTCAE v. 4.0 manual, go to <http://ctep.cancer.gov/reporting/ctc.html>

ATTRIBUTION DEFINITIONS

Adverse events will be categorized for their relation to one or more of the following:

- bone marrow transplantation
- investigational study medication, Idelalisib
- other protocol-directed study procedures

The Principal Investigator will do the initial determination of the relation, or attribution, of an AE to study participation and will record the initial determination on the appropriate eCRF and/or SAE reporting form. The relation of an AE to study participation will be determined using definitions in Table 1.

TABLE 1: ATTRIBUTION OF ADVERSE EVENTS

Code	Descriptor	Relationship (to primary investigational product and/or other concurrent mandated study therapy)
Unrelated Categories		
1	Unrelated	The adverse event is clearly not related.
2	Unlikely	The adverse event is unlikely related.
Related Categories		
3	Possible	The adverse event has a reasonable possibility to be related; there is evidence to suggest a causal relationship.
4	Probable	The adverse event is likely related.
5	Definite	The adverse event is clearly related.

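### The Section 6 safety rule has no mortality-specific or between-look trigger: two deaths in the first 10 idelalisib patients, with no other event in either arm, would not reach its 75% threshold

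*Combined protocol and SAP*

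**What the plan says.** Section 6 (interim analyses) sets the schedule: "Monitoring will occur in groups of 15 patients, beginning after the first 10 enrolled on Arm A". The criterion is that the posterior probability of a "treatment-limiting toxicity in Arm A exceeding Arm B by 0.10 is 75% or greater". Meeting it leads to a recommended safety review. The settings are given above Table 1 of that section: "Both arms prior: Beta (0.10, 0.90), assumes prior for toxicity is 10%, delta of 0.10, and 75% cutoff".

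The event monitored is a treatment-limiting toxicity (TLT). This is a study drug interruption of more than 14 days, or another CTCAE grade 3 or higher event that the dose-reduction provisions do not cover. Section 9.4.1 defines grade 5 as death. No section gives deaths their own rule.

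Two other places give a number. Section 5.1 says rules will be set up to stop the study if GVHD or another toxicity leads to discontinuation at a rate more than 10% different from placebo. Section 8.2 refers to Section 6 but words the condition as a difference above 10% in toxicities of any kind. Neither gives look times or a probability threshold.

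Oversight is described in Section 9.1: "All data will be reviewed periodically by the SKCCC Safety Monitoring Committee (SMC), which may provide recommendations". Section 9.2.3 requires deaths to be reported whatever their cause, and Section 9.5 sends serious adverse events to the IRB within 48 hours. The attribution scale in Section 9.4 runs from 1 to 5. Code 3 (possible) reads "The adverse event has a reasonable possibility to be related; there is evidence to suggest a causal relationship".

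**The concern.** This is a phase I safety trial in transplant recipients, and Sections 5.1 and 8.2 both say that novel toxicities have to be considered. A calibrated rule in such a trial should respond to the most serious outcome. This one has three gaps.

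- It gives a death no more weight than a non-fatal grade 3 event.
- It is silent before 10 patients are on Arm A, and between looks.
- At the first look its reference is about five placebo patients, so one placebo event changes the threshold markedly.

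A death might not count at all. The TLT definition leaves out events handled by dose reduction, and Section 5.2 covers pneumonitis, hepatotoxicity and diarrhea in that way. The text does not say whether a fatal case of one of these is a TLT. The calculations below assume that it is, which favours the plan.

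**Working it through.** **Inputs.** The priors, margin and cutoff are those quoted above. Arm A at the first look is 10, as stated. Arm B at 5 is inferred from "Patients will be randomized in a 2:1 ratio". The later looks, 20/10 and 30/15, follow from groups of 15 and "The maximum sample size will be 45 patients, 30 in Arm A and 15 in Arm B". Assumptions: outcomes are complete at each look, and each death counts as one TLT.

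**1. The plan's own figures.** I applied the rule as written by exact binomial enumeration over the three looks. It does not reproduce Tables 1 and 2 of Section 6. For control 0.05 and idelalisib 0.20 the plan prints 32.4% stopped. The stated rule gives 46.2% if only the first two looks can stop the trial and 58.6% if the final look counts. That mismatch is a separate matter, and no table percentage is used here as a measure of size.

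The tables do agree that 2/10 vs 0/5 does not fire. If it did, the first look alone would stop at least P(0 of 5 placebo) x P(at least 2 of 10 on Arm A):

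- at 0.05/0.10: 0.774 x 0.264 = 20.4%, against a printed total of 6.8%
- at 0.05/0.05: 0.774 x 0.086 = 6.7%, against a printed total of 1.3%

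**2. Posterior.** With x events in n patients, each arm's posterior is Beta(0.1 + x, 0.9 + n - x). The rule fires if P(pA - pB > 0.10) is at least 0.75. For 2/10 vs 0/5 the posteriors are Beta(2.1, 8.9) and Beta(0.1, 5.9), which give 0.712. For 4/10 vs 1/5 they are Beta(4.1, 6.9) and Beta(1.1, 4.9), which give 0.691.

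| Look (A/B) | Placebo TLTs | Largest Arm A count that does not fire | Smallest that fires |
|---|---|---|---|
| 10/5 | 0 | 2 (0.712) | 3 (0.902) |
| 10/5 | 1 | 4 (0.691) | 5 (0.816) |
| 20/10 | 0 | 3 (0.657) | 4 (0.843) |
| 20/10 | 1 | 5 (0.655) | 6 (0.774) |
| 30/15 | 0 | 4 (0.630) | 5 (0.804) |
| 30/15 | 1 | 6 (0.635) | 7 (0.752) |

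**3. Weight of one placebo event.** At the plan's two control rates, the chance of at least one TLT in 5 placebo patients is 1 - 0.95^5 = 0.226 or 1 - 0.90^5 = 0.410. That event moves the first-look threshold from 3 to 5. If the true Arm A rate is 30%, the chance of firing at that look is P(Bin(10, 0.30) >= 3) = 0.617 with no placebo event and P(Bin(10, 0.30) >= 5) = 0.150 with one.

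**4. Section 6 against Sections 5.1 and 8.2.** For 2/10 vs 0/5 the observed difference is 20 points. That exceeds the 10% in Section 8.2, and also the 10% in Section 5.1 if the deaths are counted as discontinuations. Section 6 does not fire on the same data. The consequences differ too: Section 6 recommends a review, while the other two speak of stopping the study. The plain differential also depends on placebo: 3/10 vs 1/5 is 30% against 20%, exactly 10 points and so not above 10%.

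**5. Time before the first look.** At 20 patients a year, 15 patients take 15/20 x 12 = 9 months to enrol.

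**The case against.** The strongest reply is that the plan has more protection than Section 6 alone. Sections 5.1 and 8.2 state a differential that the two-death case would exceed. The committee sees all data and may recommend termination. Serious events must go promptly to investigators, IRBs and health authorities. The trial also runs under an institutional monitoring plan (Section 10.5), whose text is not in these documents. All of this stands. A reader might infer that Section 6 is the only numeric trigger, or that two deaths would go unreviewed. The documents support neither. What they support is that nothing in this protocol makes a review or a hold obligatory after such a death.

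The headline case is also specific: it needs no TLT in the other eight Arm A patients. One more, with none on placebo, gives 0.902 and fires. If each of the eight has a 10% risk (the prior mean), the chance of at least one more is 1 - 0.9^8 = 57%. The four-death case likewise needs the other six to be event-free. Nor does one placebo event disable the rule; it raises the bar.

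A reader might also subtract the printed stopping rates from 100% and conclude that a 20-point excess goes unstopped in 46.9% (0.05 vs 0.25) or 41.0% (0.10 vs 0.30) of trials. The stated rule gives 24.0% and 27.0% with the final look counted, or 36.6% and 37.3% without it. Those figures concern all TLTs, not deaths, and do not bear on this point.

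Finally, the choice of attribution codes, time window and hold is a judgement that the documents do not dictate, and the frequency of pauses cannot be estimated from them. That is fair, and it is why this is offered as a cheap improvement rather than the correction of an error.

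**Conclusion.** The gap is real but bounded. As written, the Section 6 rule does not fire at 2/10 vs 0/5 (0.712) or 4/10 vs 1/5 (0.691), even if every one of those Arm A events is a death. It has no trigger before or between looks and none specific to mortality. Sections 5.1 and 8.2 would give a different answer on the same data, so the three sections must be reconciled.

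The result rests on five Arm B patients at the first look (inferred), complete outcomes, deaths counted as TLTs, and no other Arm A TLT. It describes this protocol only; the institutional monitoring plan may add obligations that cannot be seen here. The change is worth making because it is small and concerns the most serious outcome.

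**What to change.** Keep the Bayesian rule. Add one sentence to Section 6, cross-referenced in Section 9.1: any grade 5 event attributed to study drug as possible, probable or definite (codes 3 to 5 in the Section 9.4 table), from first dose through the 30-day post-dose visit, goes promptly to the existing Safety Monitoring Committee, and accrual is held until that review is done, whatever the look schedule or the placebo count.

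Reconcile Sections 5.1 and 8.2 with Section 6, so that the event counted, the threshold and the consequence are the same wherever the stopping rule is described.

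The cost is one sentence, a cross-reference and an edit to two paragraphs, with no new committee, staff or patients. The downside is an occasional short accrual pause, including for a placebo patient's death that is attributed to drug while blinded. The added trigger governs trial review and accrual only; no dose or patient-level treatment rule changes.

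### Tables 1 and 2 do not follow from the stopping rule printed with them, and the size and direction of the error depend on follow-up handling the plan does not state

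*Combined protocol and SAP*

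**What the plan says.** All of this is in Section 6, Study Statistics. The treatment-limiting toxicity probability in each arm "will follow a Beta (0.10, 0.90) prior distribution". The interim paragraph says the study will "evaluate whether to hold accrual after fixed cohorts of patients" and sets the looks: "Monitoring will occur in groups of 15 patients, beginning after the first 10 enrolled on Arm A". The maximum is 30 on Arm A and 15 on Arm B, randomized 2:1. The trigger is that the "posterior probability of a treatment-limiting toxicity in Arm A exceeding Arm B by 0.10 is 75% or greater". The consequence is stated as follows: "The stopping rule will recommend a safety review".

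The same paragraph introduces the tables as "Operating characteristics of the study with Arm B treatment-limiting toxicity of either 5%, Table 1, or 10%, Table 2". The scenarios with "varying toxicities in Arm A are based on 1,000 simulations of the trial". The heading of Table 1 repeats the settings ("Both arms prior: Beta (0.10, 0.90), assumes prior for toxicity is 10%, delta of 0.10, and 75% cutoff"), and the heading of Table 2 repeats them again. The prior therefore appears four times, always the same.

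The endpoint covers day 90 to day 270, and expected accrual is 20 patients per year. The plan does not say whether the evaluation at 45 patients counts as a stop, or how a patient who has not reached day 270 enters the posterior. It prints no event-count boundaries.

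**The concern.** The prior, margin, cutoff, group size and number of simulations are all printed, so the tables can be checked from the document alone. When the printed rule is worked through, half or more of the stop probabilities lie well outside simulation error under the plainest readings.

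Safety is the primary goal of the trial, and these two tables are the only evidence of how often the safety rule would fire at a given true toxicity difference. Whoever approves or oversees the trial would judge the rule by figures that it does not produce.

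**Working it through.** **Inputs (Section 6).** Prior Beta(0.10, 0.90) in each arm; margin 0.10; cutoff 0.75; groups of 10 Arm A + 5 Arm B; maximum 30/15; 1,000 simulations per scenario.

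**Formulas.** With xA events in nA and xB in nB, the posteriors are pA ~ Beta(0.10 + xA, 0.90 + nA − xA) and pB ~ Beta(0.10 + xB, 0.90 + nB − xB). Trigger when P(pA − pB > 0.10) ≥ 0.75. With s1 and s2 the exact probabilities of stopping at looks 1 and 2, the stop probability is p = s1 + s2, average Arm A size is 30 − 20·s1 − 10·s2, and the simulation SE of p is √(p(1 − p)/1000), at most 1.6 points.

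**Boundaries from the printed rule, for 0, 1, 2 Arm B events.** Look 1 (10/5): 3, 5, 7 Arm A events. Look 2 (20/10): 4, 6, 9. For example, 4/20 v 0/10 gives Beta(4.1, 16.9) against Beta(0.1, 10.9) and a posterior probability of 0.84, so it triggers.

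**A row that agrees.** At (Arm B 0.05, Arm A 0.05) the plan states 1.3% and 29.8 patients; the exact values are 1.5% and 29.8.

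**The worst row.** At (0.05, 0.20), s1 = 25.6% and s2 = 20.6%.
- p = 46.2%, against 32.4% stated.
- SE = √(0.462 × 0.538/1000) = 1.58 points, so the gap of 13.8 points is nearly 9 SE.
- Average Arm A size = 30 − 20 × 0.256 − 10 × 0.206 = 22.8, against 24.7 stated.

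**Rows beyond 3 SE (complete outcomes, looks at 10/5 and 20/10).**

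| Arm B, Arm A | Stated | Exact |
|---|---|---|
| 0.05, 0.10 | 6.8% | 10.6% |
| 0.05, 0.15 | 19.2% | 27.2% |
| 0.05, 0.20 | 32.4% | 46.2% |
| 0.05, 0.25 | 53.1% | 63.4% |
| 0.05, 0.30 | 68.2% | 76.6% |
| 0.05, 0.35 | 82.3% | 85.9% |
| 0.10, 0.15 | 12.0% | 19.3% |
| 0.10, 0.20 | 27.9% | 34.3% |
| 0.10, 0.25 | 44.3% | 49.4% |

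All nine are understated. The row (0.10, 0.10), 4.9% v 7.3%, is just under 3 SE. The last three rows of Table 2 are stated 1.5 to 1.9 points too high, within 3 SE. Average Arm A size misses by more than 3 SE in 8 rows, by at most 1.9 patients.

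**Other readings with complete outcomes and the printed prior, margin and cutoff (stop rows beyond 3 SE, of 18).**
- The 45-patient look also counts: 17; (0.05, 0.20) becomes 58.6%.
- Arm A compared with the posterior mean of Arm B plus 0.10: 12 with two looks, 17 with three.
- Second look at 25 on Arm A, another way to read the schedule: 12 with 12 on Arm B, 11 with 13. Average size then misses in at most 1 row, but the stop column still fails.
- 2:1 allocation not balanced within groups: 12 with two looks, 18 with three.
- First look only: 14, with the tables too high.

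**Incomplete follow-up.** At 20 per year, about 20 × 180/365 = 9.9 patients enrol in any 180 days, so roughly 10 of the 15 patients at look 1 have not finished the window. I simulated the printed rule with looks at enrolment of patients 15 and 30 and unseen toxicities counted as non-events (100,000 trials per row). The plan gives no event timing, so I assumed events uniform over a window after enrolment, with arrivals evenly or randomly spaced.

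| Event window | Stop rows missed, even / random arrivals | Direction of misses | Size rows missed, even / random |
|---|---|---|---|
| 30 days | 7 / 8 | mixed | 1 / 3 |
| 84 days | 5 / 4 | mixed | 7 / 10 |
| 120 days | 3 / 8 | all overstated | 11 / 13 |
| 180 days | 9 / 12 | all overstated | 17 / 18 |

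With the 180-day window, (0.05, 0.20) comes to 31% to 33%, close to the stated 32.4%, while (0.10, 0.50) falls to 86% to 87% against 94.4% stated. The counts shift by several rows with details such as arrival spacing, so only the range should be relied on. None of these variants reproduces both columns.

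**The case against.** The strongest objection is that complete outcomes is an assumption, and not the one most favourable to the tables. The looks are tied to enrolment, and at the planned accrual most patients at the first look are still in the window. Under some assumed event timings fewer than nine stop rows miss, and the direction reverses. This stands. A reader might infer that the tables uniformly understate how often the rule fires, or that nine is the smallest possible number of misses. The plan supports neither, because both statements hold only under stated follow-up handling. The objection does not rescue the tables: where the stop column improves, average sizes still miss.

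A reader might also infer that a different rule was used. One with a Beta(0.5, 4.5) prior and a comparison with the posterior mean of Arm B fits all 18 rows in both columns. It is only a computational note. That rule was found by searching 640 combinations, another combination also fits both columns, and neither is printed. It does not show what was simulated. Nor does it show that the oversight committee cannot tell which boundary applies: the printed rule is explicit, and its boundary can be computed for complete outcomes.

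Finally, the practical effect is bounded. A trigger leads to a safety review, the equal-rate rows are within 3 SE under complete outcomes with two looks, and Arm A exposure on that reading changes by at most 1.9 patients. This also stands, and it limits the severity.

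**Conclusion.** The concern holds in this form: the operating characteristics in Tables 1 and 2 are not those of the printed rule. Under complete outcomes with stops only at 15 and 30 patients, 9 of 18 stop probabilities miss by more than 3 simulation SE, by up to 13.8 points and all understated, and 8 average sizes miss. Counting the 45-patient look raises the stop-probability misses to 17. With unseen toxicities as non-events the count and direction change, under event timing that I had to assume. No reading tested with the printed prior, margin and cutoff reproduces both columns.

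The documents do not show whether the tables, the printed settings or an unstated treatment of follow-up is the source. The point should be fixed, but its consequence is moderate. Confidence in the mismatch is high; there is no basis for a single direction of error.

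**What to change.** Re-run the simulation with the printed rule and replace both tables. If a different prior weight, comparison, cutoff or look schedule was used, correct the printed rule to match the simulation instead. In either case:

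- state whether the 45-patient evaluation counts as a stop;
- state how patients who have not reached day 270 enter the posterior, and simulate under that handling, with the assumed event timing and accrual given;
- print the event-count boundary at each look (Arm A events for each Arm B count).

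The cost is a few hours of re-simulation and replaced figures or a corrected rule sentence, with no extra patients. If the sponsor chooses to wait for day 270 at each look, looks come later or accrual pauses.
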